4.2. Clinical Procedures and Evaluations

Evaluation of this investigational vaccine will include laboratory tests, medical history, physical assessment by clinicians and subject self-assessment. The schedule of study visits is shown in

the Schedule of Evaluations ([Appendix III](#)). Total blood volume drawn from each subject will not exceed 550 mL in any 8 week period.

4.2.1. Screening

Screening for this study will be completed through the VRC's screening protocol, VRC 500 (NIH 11-I-0164). Subjects will be recruited through Institutional Review Board (IRB)-approved advertising. Evaluations and sample collections for screening processes include a medical history review, physical exam, any laboratory tests needed to confirm eligibility, and pregnancy test for women of reproductive potential. If screening evaluations suggest a concerning health condition, appropriate evaluations should be conducted based on clinical judgment. Screening evaluations for specific eligibility criteria must be completed within the time interval specified prior to enrollment for the given parameter and may be repeated, as needed, to confirm eligibility. Blood samples for research must be collected during screening; although generally collected in the 56 days prior to enrollment, a particular interval of time prior to enrollment for collection of these samples is not specified.

The informed consent form (ICF) will be reviewed and counseling related to pregnancy prevention will be provided. Subjects who are not up to date on standard vaccinations may receive these, if available, during screening or at a later date during study participation. As part of the informed consent process, an Assessment of Understanding (AoU) is completed on the day the subject is scheduled to enroll, prior to signing the VRC 317 ICF. Incorrect answers will be explained by the study clinician, and the VRC 317 ICF may be signed once the clinician is satisfied with the subject's understanding of the study.

4.2.2. Enrollment

Day 0 is defined as the day of protocol enrollment and first study injection. Protocol-specific eligibility is reviewed on Day 0 as part of the enrollment process, but eligibility evaluations conducted during a screening visit are routinely used for eligibility if the screening occurred within the specified window prior to the Day 0 visit. However, if clinical assessment on Day 0 suggests significant changes may have occurred since the screening visit, then evaluations done on Day 0 are used for eligibility. Day 0 evaluations and medical history prior to the first injection are the baseline for subsequent safety assessments.

4.2.3. Product Administration

On each injection day (prior to injection), laboratory and research samples will be collected and subjects will be clinically evaluated. A subject who arrives at the clinic with fever or evidence of an acute illness, which precludes administration of the vaccine, may be rescheduled within the allowed visit window. Pregnancy test results for females of reproductive potential must be confirmed as negative within 24 hours before each injection.

When choosing a site for injection, clinicians should consider whether there is an arm injury, local skin problem or significant tattoo that precludes administering the injection or will interfere with evaluating the arm after injection. It is recommended, but not required, that the first injection be administered into the non-dominant arm. It is preferred, but not required, to alternate arms for study injections.

All injections will be administered IM into upper arm deltoid muscle by needle and syringe. For groups receiving adjuvant, the adjuvant will be field mixed by the site pharmacist prior to administration.

4.2.4. Post-Injection Follow-Up and Diary Card

Post-Injection Follow-Up: Following each study injection, subjects will be observed for a minimum of 60 minutes. Vital signs (temperature, blood pressure and pulse) will be taken at least 60 minutes post-injection. The injection site will be inspected for evidence of local reaction. In keeping with the institution's policy and good medical practice, acute medical care will be provided to subjects for any immediate allergic reactions or other injury resulting from participation in this research study.

Study clinicians must inform subjects to contact the clinic at any time after each study injection if the subject has any concerning signs or symptoms. Follow-up on subject well-being will be performed by telephone on the first or second day following all injections and by clinic visits as shown in the Schedule of Evaluations (Appendix III).

Events following any study injection that may require clinical evaluation include rash, urticaria, fever of 38.5°C (Grade 2) or higher lasting greater than 24 hours, or significant impairment in the activities of daily living. Other clinical concerns may prompt a study visit based on clinical judgment.

Oral and nasal mucosal samples will be collected at specified study visits according to the Schedule of Evaluations in Appendix III. A small ophthalmic sponge designed for clinical use will be used to collect oral mucosal samples. Flocked swabs will be used to collect the nasal mucosal samples. These samples are for research purposes only and are not used for evaluating subject health.

Diary Card: Subjects will be given a "Diary Card" to use as a memory aid, on which to record temperature and symptoms daily for 7 days after each injection. Subjects will be trained and encouraged to use the secure electronic database, but will also have the option to complete a paper diary card. When the diary card parameters are recorded directly by the subject in the electronic database, the subject's electronic record will be the source for these data. When collected, the paper diary card will be used as a source document. When neither a paper nor electronic diary is available from the subject, the clinician will document the source of reactogenicity information recorded in the study database.

The solicited signs and symptoms on the diary card will include the following parameters: unusually tired/feeling unwell, muscles aches (other than at injection site), headache, chills, nausea, and pain/tenderness at injection site. Subjects will also record the day's highest measured temperature and measurement of largest diameter for redness and swelling at injection site.

4.2.5. Follow-Up through End of Study

Study follow-up will continue via clinical visits through 44 weeks after the first study injection. The visit schedule is based on intervals of time after each study injection administration. Any subject who receives at least one study injection (including those subjects who elect not to

receive the optional second dose) will be expected to continue with follow-up for safety and immunogenicity through study Week 44 as per Schedule of Evaluations (Appendix III).

Throughout the study, any subject who is suspected of having an upper respiratory infection based on the presence of rhinorrhea in conjunction with at least one additional sign and/or symptom should be evaluated by nasal flock swab for PCR diagnostic purposes.

The schedule of visits, allowable windows for completing the visits, and evaluations performed at each visit are shown in the Schedule of Evaluations in Appendix III. After Day 0, deviations from the visit windows in completing study visits are discouraged and will be recorded as protocol deviations, but are permitted at the discretion of the PI.

4.2.6. Concomitant Medications

Only routine prescription medications at the time of enrollment are recorded in the study database. Subsequently, concomitant medications are only updated or recorded in the study database if there is an occurrence of an adverse event (AE) that requires expedited reporting or if the subject develops a new chronic condition that requires ongoing medical management. Receipt of a FDA-approved vaccine at any time during the study will be recorded in the database (clinicians should work with subjects regarding the timing of licensed vaccines relative to study injection). Otherwise, the concomitant medication changes throughout the study will be recorded in the subject's chart as needed for general medical records, but will not be recorded in the study database.

4.3. Dose Continuation and Dose Escalation Plans

Dose groups will be enrolled sequentially, with no more than one subject per day for the first 2 study injections of the study. Dose continuation and escalation will occur after subjects have completed the first injection and following interim safety data reviews. Approval to proceed will be obtained from the Protocol Safety Review Team (PSRT).

- The dose continuation review (for 50 mcg) will occur when at least 5 subjects who received 50 mcg in either Group 1 or Group 2 have completed post-injection follow-up through completion of the 7 day diary card. If assessed as safe to continue, enrollment of additional subjects in Group 1 and Group 2 may proceed.
- The first dose escalation review (50 mcg to 150 mcg) will occur when at least 10 subjects who received 50 mcg in either Group 1 or Group 2 have completed post-injection follow-up through at least the "Study Week 2" visit. If assessed as safe, enrollment of additional subjects may proceed until at least 10 subjects have enrolled in each Group 1 and Group 2. After that, enrollments may begin in Group 3 and Group 4.
- The second dose escalation review (150 mcg to 500 mcg) will occur when at least 10 subjects who received 150 mcg in either Group 3 or Group 4 have completed post injection follow-up through at least the "Study Week 2" visit. If assessed as safe, enrollment of additional subjects may proceed until at least 10 subjects have enrolled in each Group 3 and Group 4. After that enrollments may begin in Group 5 and Group 6.

- The final dose continuation review (for 500 mcg) will occur when at least 10 subjects who received 500 mcg in either Group 5 or Group 6 have completed post injection follow-up through at least the “Study Week 2” visit. If assessed as safe, enrollment of additional subjects may proceed until at least 10 subjects have enrolled in each Group 5 and Group 6.
- The second injection for all groups may occur once the first dose of that dose level has been assessed as safe at the “Study Week 2” visit.

If the first study injection is not completed or there are discontinuations from the study before there are sufficient data to conduct the dose escalation review for a group, then extra subjects may be enrolled into that group in order to have the requisite data on at least 10 subjects. Additionally, AEs assessed as related to the study product at the time of a dose escalation review may be judged by the PSRT to warrant adding additional subjects at a given dose level.

The IRB will be provided with documentation of the safety review process and notification of the dose escalation. Consultation with the IRB and FDA, if needed, as per study pause criteria ([Section 4.4](#)) will occur if indicated by the review. One outcome of a dose escalation review may be to recommend evaluation of additional subjects at the current dose level and reassess for safety before proceeding to a higher dose level.

4.4. Criteria for Discontinuing Subject Participation

Decisions to discontinue study injections or protocol participation for a subject will be made by the PI.

4.4.1. Discontinuation from Study Injections

A subject may be discontinued from study injections for the following reasons:

- Pregnancy;
- Grade 3 AE assessed as related to study product (except that self-limited Grade 3 solicited reactogenicity does not require discontinuation of injections);
- Grade 4 AE assessed as related to study product;
- Immediate hypersensitivity reaction associated with study product;
- Intercurrent illness that is not expected to resolve before the next scheduled injection;
- Treatment with systemic glucocorticoids (e.g., prednisone or other glucocorticoid) or other immunomodulators (other than nonsteroidal anti-inflammatory drugs [NSAIDs]), with the exception that study injection may continue per PI discretion if the next one occurs at least 2 weeks following completion of glucocorticoid treatment; or,
- The PI assesses that it is not in the best interest of the subject to continue receiving study product.

4.4.2. Discontinuation from Protocol Participation

A subject may be discontinued from protocol participation for the following reasons:

- Subject voluntarily withdraws;
- The IND Sponsor or regulatory authorities stop the study; or,
- The PI assesses that it is not in the best interest of the subject to continue participation in the study or that the subject's compliance with the study is not sufficient.

4.5. Criteria for Pausing and Resuming the Study

4.5.1. Criteria for Pausing the Study

The PI and PSRT will closely monitor and analyze study data as they become available and will make determinations regarding the presence and severity of AEs. Enrollments and administration of study product will be paused by the PI, and the IND Sponsor will be promptly notified, according to the following criteria:

- **One** (or more) subject experiences a **Serious Adverse Event (SAE)** assessed as related to study product.
- **Two** (or more) subjects experience the same **Grade 3 or higher unsolicited AE** assessed as related to the study product.

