5. SAFETY AND ADVERSE EVENTS

5.1. Adverse Events

An adverse event (AE) is any untoward or unfavorable medical occurrence in a human subject, including any abnormal sign (e.g., abnormal physical exam or laboratory finding), symptom, or disease temporally associated with the use of study treatment, whether or not considered related to the study treatment.

AEs will be graded according to the Table for Grading Severity of AEs ([Appendix IV](#)). The following guidelines will be used to determine if an AE should be recorded in the database:

- Solicited AEs (i.e. reactogenicity parameters) will be recorded in the study database for 7 days after each study injection without the collection of product attribution assessments.

Clinicians will follow and collect resolution information for any reactogenicity symptoms that are not resolved within 7 days.

- Unsolicited AEs will be recorded in the study database from the date of receipt of each study injection through the visit scheduled at 28 days after each injection with the collection of product attribution assessments. At other time periods between injections and when greater than 28 days after the last injection, only SAEs (as detailed in [Section 5.2](#)) and new chronic medical conditions will be recorded as an AE through the last study visit.

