6.4.2. Safety Analysis

Reactogenicity: The number and percentage of subjects experiencing each type of reactogenicity sign or symptom will be tabulated by severity. For a given sign or symptom, each subject's reactogenicity will be counted once under the maximum severity for all assessments.

Adverse Events: AEs will be coded into Medical Dictionary for Regulatory Activities (MedDRA) preferred terms. The number and percentage of subjects experiencing each specific AE will be tabulated by severity and relationship to study product. For the calculations in these tables, each subject's AE will be counted once under the maximum severity or strongest recorded causal relationship to treatment.

A complete listing of AEs for each subject will provide details including severity, relationship to treatment, onset, duration and outcome.

Safety Laboratory Values: Boxplots of local laboratory values will be generated for baseline values and for values measured during the course of the study. Each boxplot will show the 1st quartile, the median, and the 3rd quartile. Outliers, or values outside the boxplot, will also be plotted. If appropriate, horizontal lines representing boundaries for abnormal values will be plotted.

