8.8. Safety Monitoring

8.8.1. Protocol Safety Review Team

Close cooperation between the designated members of the Protocol Team will occur to evaluate and respond to individual AEs in a timely manner. Study clinicians will conduct a daily safety review of any new clinical data. The PSRT includes designated team members (PI, Associate Investigators, Study Coordinators, Protocol Specialist, and other study clinicians). The PSRT will review the summary study safety data reports on a weekly basis through 4 weeks after the last subject receives the final study injection in order to be certain that the vaccine has an acceptable safety profile, and will continue to monitor the study safety data reports on at least a monthly basis through completion of the study.

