9.3. Data Collection, Data Sharing, and Protocol Monitoring

9.3.1. Data Collection

Clinical research data will be collected in a secure electronic web-based clinical data management system. Extracted data without subject identifiers will be sent to the protocol statistician for statistical analysis as needed.

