Visit windows: Visits 02A, 06A (+1 day); Visit 02B (± 1 day); Visit 02C, 06C (-2 days); Visit 03, 04, 05, 07, 08 (± 3 days); Visit 06 (± 7 days); and Visit 09, 10, 11 (± 7 days). Schedule Visits 02A-06 relative to Visit 02, Visits 06A-11 relative to Visit 06.

**APPENDIX IV: ASSESSMENT OF RELATIONSHIP TO VACCINE AND
ADVERSE EVENT SEVERITY GRADING**

Assessment of Causality Relationship of an Adverse Event to Study Vaccine:

The relationship between an adverse event (AE) and the vaccine will be assessed by the investigator on the basis of his or her clinical judgment and the definitions below.

- **Definitely Related.** The AE and administration of study product are related in time, and a direct association can be demonstrated.
- **Probably Related.** The AE and administration of study product are reasonably related in time, and the AE is more likely explained by study product than other causes.
- **Possibly Related.** The AE and administration of study product are reasonably related in time, but the AE can be explained equally well by causes other than study product.
- **Not Related.** There is not a reasonable possibility that the AE is related to the study product.

For purposes of preparing data reports in which AE attributions are limited to “**Related**” or “**Not Related**”, in this protocol, the “Definitely, Probably and Possibly” attributions will be mapped to the “Related” category. The definitions that apply when these two categories alone are used are as follows:

- **Related** – There is a reasonable possibility that the AE may be related to the study product.
- **Not Related** – There is not a reasonable possibility that the AE is related to the study product.

Grading the Severity of Adverse Events:

The FDA Guidance for Industry (September 2007): “Toxicity Grading Scale for Healthy Adult and Adolescent Volunteers Enrolled in Preventive Vaccine Clinical Trials” is the basis for the severity grading of AEs in this protocol. Several modifications were made to the table as follows:

- “Emergency room visit” is not automatically considered a life-threatening event; these words have been removed from any “grade 4” definition where they appear in the table copied from the guidance document.
- Any laboratory value shown as a “graded” value in the table that is within the institutional normal range will not be severity graded or recorded as an AE.

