- Severity grading for hemoglobin decrease on the basis of the magnitude of decrease from baseline is not applicable at the grade 1 level; only absolute hemoglobin will be used to define grade 1 decrease. Increases in hemoglobin are AEs only for values above the upper limit of normal and are graded by the systemic illness clinical criteria.
- Severity grading definition for Grade 4 local reaction to injectable product (Erythema/Redness and Induration/Swelling) included added text “requiring medical attention”.
- 1 X ULN was removed from the definition for PT increase.

When not otherwise specified in the table, the following guidance will be used to assign a severity grade:

Grade 1 (Mild): No effect on activities of daily living

Grade 2 (Moderate): Some interference with activity not requiring medical intervention

Grade 3 (Severe): Prevents daily activity and requires medical intervention

Grade 4 (Life-threatening): Hospitalization; immediate medical intervention or therapy required to prevent death.

Grade 5 (Death): Death is assigned a Grade 5 severity.

Only the single AE that is assessed as the primary cause of death should be assigned “Grade 5” severity.

**Toxicity Grading Scale for Healthy Adult and Adolescent Volunteers Enrolled in
 Preventive Vaccine Clinical Trials
 FDA Guidance - September 2007**

A. Tables for Clinical Abnormalities

Local Reaction to Injectable Product	Mild (Grade 1)	Moderate (Grade 2)	Severe (Grade 3)	Potentially Life Threatening (Grade 4)
Pain	Does not interfere with activity	Repeated use of non-narcotic pain reliever > 24 hours or interferes with activity	Any use of narcotic pain reliever or prevents daily activity	Hospitalization
Tenderness	Mild discomfort to touch	Discomfort with movement	Significant discomfort at rest	Hospitalization
¹ Erythema/Redness	2.5 – 5 cm	5.1 – 10 cm	> 10 cm	Necrosis or exfoliative dermatitis requiring medical attention
² Induration/Swelling	2.5 – 5 cm and does not interfere with activity	5.1 – 10 cm or interferes with activity	> 10 cm or prevents daily activity	Necrosis requiring medical attention
³ Vital Signs				
	Mild (Grade 1)	Moderate (Grade 2)	Severe (Grade 3)	Potentially Life Threatening (Grade 4)
⁴ Fever (°C) (°F)	38.0 – 38.4 100.4 – 101.1	38.5 – 38.9 101.2 – 102.0	39.0 – 40 102.1 – 104	> 40 > 104
Tachycardia - beats per minute	101 – 115	116 – 130	> 130	Hospitalization for arrhythmia
⁵ Bradycardia - beats per Minute	50 – 54	45 – 49	< 45	Hospitalization for arrhythmia

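### The two-subject pause rule for related severe adverse events has no time limit, but recording of non-serious events stops at the Day 28 visit after each injection

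*Combined protocol and SAP*

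**What the plan says.** Section 4.5.1 has two pause criteria. One is a single related SAE. The other is met when two or more "subjects experience the same Grade 3 or higher unsolicited AE assessed as related to the study product". Neither carries a limit on days since injection.

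Section 5.1 decides what is entered in the study database. Unsolicited AEs are recorded with product attribution from each injection through the visit 28 days later. After that the rule narrows: "At other time periods between injections and when greater than 28 days after the last injection, only SAEs" and new chronic conditions are recorded as AEs, through the last visit.

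The AE analysis in Section 6.4.2 is a set of tables: "The number and percentage of subjects experiencing each specific AE will be tabulated by severity and relationship to study product". Its source is described in Section 9.3.1: "Extracted data without subject identifiers will be sent to the protocol statistician for statistical analysis as needed".

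Appendix IV gives the default severity definitions, including "Grade 3 (Severe): Prevents daily activity and requires medical intervention". Default Grade 4 means hospitalization, or immediate intervention to prevent death.

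Injection 2 is planned for Week 12. Under Section 4.3 it may go ahead at a dose level once the first injection there has been judged safe at the Week 2 visit.

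**The concern.** The pause rule counts a class of event that the recording rule stops collecting part-way through the interval the pause rule protects. The two-subject criterion is the only cross-subject pause trigger for severe events that are not serious, in a first-in-human trial. Clearance for injection 2 uses Week 2 data, and no further formal go/no-go review is scheduled before Week 12, so the pause rule is the standing safeguard over the second injection.

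If one subject has a related Grade 3 event at Week 6 and another has the same event at Week 9, neither has a planned AE record. The plan does not say how the two would be matched and counted. Either 4.5.1 was meant to lapse after the Day 28 visit, which it does not say, or the recording plan falls short of it.

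Safety reporting is also affected. AEs are a primary endpoint under Section 6.2.1, and late events of this kind would not appear in the AE tables.

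**Working it through.** **The plan's nearest figure.** The documents give no length for the gap. The closest stated number is in Table 2: a probability of 0.23 of two or more events among 90 subjects at a 1% rate. It reproduces: 1 − 0.99^90 − 90 × 0.01 × 0.99^89 = 1 − 0.40473 − 0.36794 = 0.2273. The arithmetic of two-event counts in the plan is sound. The question is which events reach the count.

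**Inputs (Appendix III).**
- Visit 04: D28 ± 3 days.
- Visit 06 (injection 2): D84 ± 7 days.
- Visit 08: 28 days after injection 2, ± 3 days.
- Visit 11: D308, which is 308 − 84 = 224 days after injection 2, ± 7 days.

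**Gap before injection 2.**
- Nominal: 84 − 28 = 56 days; 56/84 = 67%.
- Shortest: 77 − 31 = 46 days; 46/77 = 60%.
- Longest: 91 − 25 = 66 days; 66/91 = 73%.

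By design this applies to subjects who receive injection 2. It is optional for the last 5 in each of 6 groups, so that is 90 − 30 = 60 up to 90 of the 90 planned.

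**Gap after the last Day 28 visit.** This bears on safety reporting throughout, and on the pause rule only while other subjects remain to be dosed.
- Two injections: 224 − 28 = 196 days nominal; 217 − 31 = 186 shortest; 231 − 25 = 206 longest.
- One injection: 308 − 28 = 280 days nominal.

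**Which events fall in the gap.** SAEs and new chronic conditions are always recorded. Default Grade 4 normally meets the SAE definition, so what remains is mainly non-serious, non-chronic Grade 3. These are mostly clinical events, because Appendix III schedules no CBC, creatinine or ALT between D28 and D84 or after D112.

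**Why the days do not convert to a probability.** Let f be the share of qualifying events that start inside the recording window. The documents do not give f. As an illustration only, assume a 5% per-subject rate of the same qualifying event up to injection 2, among 30 subjects (one dose level). The chance that two or more enter the AE database is then:

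| f (assumed) | P(2 or more recorded) |
|---|---|
| 1 | 0.446 |
| 0.9 | 0.394 |
| 0.75 | 0.311 |
| 0.5 | 0.172 |
| 1/3 | 0.089 |

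These are chances of two database records. They are not chances of a pause being called or missed, since clinical review can also bring cases to the PI. If most related events start early, f is near 1 and the loss is small.

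**The case against.** The strongest reply is that the two sections do different jobs. Section 4.5.1 tells the PI and PSRT to monitor study data as they arrive and to determine the presence and severity of AEs; it does not tie the pause to the AE database. Section 5.1 governs only what is entered there. Much else continues after Day 28:

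- Appendix III schedules medical histories at D56, D84, D168, D252 and D308, and Section 4.2.3 requires clinical evaluation before each injection.
- In Appendix IV, "The relationship between an adverse event (AE) and the vaccine will be assessed by the investigator", with no day limit.
- Section 8.8.1 states: "Study clinicians will conduct a daily safety review of any new clinical data". It adds weekly PSRT review through four weeks after the last subject's final injection.
- Section 4.4.1 lets the PI stop a subject's injections for one related Grade 3 AE, at any time. The same PI applies the pause.
- Section 5.3.1 sends unanticipated problems to the IRB within 7 days.

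This stands as an answer to any claim that late events go unseen. It does not supply a planned count across subjects. Each safeguard can surface a single case, and unanticipated-problem reporting applies a different test: the event must be unexpected and suggest greater risk.

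A reader might draw stronger conclusions that the documents do not support:

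- That treatment data are lost because of the 28-day limit. The restriction on concomitant medications in Section 4.2.6 applies equally inside the window, so it is not a consequence of this gap.
- That late events could not be recovered from any study data. Section 9.3.1 says clinical research data are collected electronically, and no section says whether visit histories are entered. Only the absence of a planned AE record is established.
- That PSRT reports omit these events. The documents do not say what those reports are drawn from.

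Timing also counts against the point. By 8 August 2019, 95 of at most 100 subjects were enrolled and escalation was complete (Section 1.3). Subjects enrolled by then would, on schedule, be past injection 2 by about 7 November 2019 (91 days later).

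**Conclusion.** The mismatch is real and can be read directly from Sections 4.5.1 and 5.1. For nominally 56 of the 84 days before injection 2 (60% to 73% of the interval across visit windows), and after the last Day 28 visit while others remain to be dosed, a related Grade 3 event that is neither serious nor chronic has no planned AE record, recorded attribution or cross-subject tally. Such events also stay out of the Section 6.4.2 AE tables.

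The conclusion is limited to recording and counting. Someone might take 67% as the chance of missing a pause, or doubt the statement in Section 1.3 that no pausing rule was met. Neither follows. The figure is a length of time, the documents give no onset distribution, and nothing in them suggests that qualifying events occurred unnoticed.

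The prospective value for the pause rule is small, since at most 100 − 95 = 5 subjects remained to enroll. What is left is mainly completeness of the final safety report, plus agreement between two rules that should cover the same events. That justifies a low-cost amendment.

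**What to change.** Make three linked edits.

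1. **Section 5.1, last sentence.** Provide that, outside the 28-day windows, SAEs, new chronic conditions and any unsolicited AE of Grade 3 or higher judged related to study product are recorded, with grade and attribution, until the final visit. Leave the 28-day window unchanged for everything else.
2. **Section 4.5.1.** Add a clause stating that these later events count toward the two-subject criterion.
3. **Section 6.4.2.** Show them in a separate row, so the 28-day percentages do not change.

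Keep the extension to related events, which is what the pause rule counts. Collecting every Grade 3 event through D308 regardless of relationship would depart from the plan's chosen window and is more open to debate.

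The cost is low. No visits are added, because the histories are already scheduled. If 1% to 10% of 90 subjects had such an event (an assumption borrowing Table 2's illustrative rates, which are not Grade 3 incidences), the extra records would number 90 × 0.01 = 0.9 to 90 × 0.10 = 9. The main drawback is that, for subjects already past Day 28, events must be abstracted from visit histories and flagged as ascertained differently.
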